6.6. Vital Signs and Physical Examination Findings

Vital signs (systolic and diastolic blood pressure, pulse, and body weight) are measured at screening visit. Vital signs are taken at a different schedule for the two treatment groups at postbaseline. For the lenalidomide only group on Day 1 of odd cycles (ie, cycles 1, 3, 5, 7, and so on). For the daratumumab plus lenalidomide group on Day 1 of cycle 1 immediately before administration, at end of administration; and at 0.5 and 1 hour after end of administration; from cycle 2 onwards: Immediately before and at the end of daratumumab administration on Day 1 of odd cycles (ie, Day 1 of cycles 3, 5, 7, and so on). The values and change from baseline of each parameter will be summarized at each scheduled time point by treatment group.

Post-baseline physical examination findings were collected as AEs, and therefore will not be summarized.

6.7. Electrocardiogram

The interpretation of the electrocardiograms (ECGs) as determined by a qualified physician (investigator or qualified designee) will be displayed by the number and percentage of subjects meeting the normality criteria. The interpretation will be summarized at baseline and the post-baseline timepoints by treatment group.

6.8. ECOG Performance Score

ECOG performance status evaluates the effect of the disease status on the activities of daily living will be assessed at screening visit, at Day 1 of old cycles. Descriptive statistics will be used to summarize ECOG performance status at baseline, scheduled post-baseline timepoints (including change from baseline) for each treatment group. Shift table from baseline to the worst score during the treatment period will be provided.

6.9. Transfusions

The number of subjects with transfusions during the study will be summarized by the type of transfusions. Also, the number of transfusions will be summarized similarly.

7. FUNCTIONAL STATUS AND WELL-BEING

7.1.1. Definition

Functional status and well-being will be assessed using three patient-reported outcomes (PROs) measure: the EORTC-QLQ-C30, EORTC-QLQ-MY20, and the EQ-5D-5L, which will be measured at baseline, 6 months, 12 months, 24 months, and 36 months. They will be scored based on the instrument developer guidelines. No imputation will be done for the PRO data.

The EORTC QLQ-C30 includes 30 items resulting in 5 functional scales (physical functioning, role functioning, emotional functioning, cognitive functioning, and social functioning), 1 Global Health Status scale (GHS), 3 symptom scales (fatigue, nausea and vomiting, and pain), and 6 single items (dyspnea, insomnia, appetite loss, constipation, diarrhea, and financial difficulties).

The instrument contains 28 items using a Likert scale with 4 response options: "Not at All," "A Little," "Quite a Bit," and "Very Much" (scored 1 to 4). Two additional items use response options (1 to 7): 1 = Very Poor, to 7 = Excellent. All scale and item scores will be linearly transformed to be in the range from 0 to 100 according to the algorithm in EORTC QLQ-C30 scoring manual, version 3.0 (Fayers et al, 2001). A higher score represents a higher ("better") level of functioning, or a higher ("worse") level of symptoms.

The EORTC Multiple Myeloma Module (QLQ-MY20) has 20-items that make up 4 scales: disease symptoms, side effects of treatment, future perspective, and body image. Scoring and interpretation are similar to the EORTC QLQ-C30.

The EQ-5D-5L is a 5-item questionnaire that assesses 5 domains including mobility, self-care, usual activities, pain/discomfort and anxiety/depression plus a visual analog scale (VAS) rating "health today" with anchors ranging from 0 (worst imaginable health state) to 100 (best imaginable health state). The scores for the 5 separate questions are categorical and cannot be analyzed as cardinal numbers. However, the scores for the 5 dimensions are used to compute a single utility score ranging from zero (0.0) to 1 (1.0) representing the general health status of the individual.

7.1.2. Analysis Methods

Analysis of PRO data will be performed on the FAS. For subjects with multiple records at the same visit, the closest one to the scheduled visit date will be selected for analysis. Compliance rates for completion of EORTC QLQ-C30, EORTC QLQ-MY20, and EQ-5D-5L at each time point will be generated based on number of received and expected. Compliance is defined as the actual number of assessments received for a visit divided by the expected number of assessments for that visit, the expected number of assessments per visit will be determined by subject-level study completion status.

The PRO endpoints are secondary and not part of the statistical hierarchy. Type 1 error control will not be applied to PRO data.

Key PRO endpoints

- EORTC-QLQ-C30 GHS, Physical Functioning, Fatigue, Pain subscales
- EORTC QLQ-MY20 Disease symptoms scale
- EQ-5D-5L utility score and VAS

Descriptive statistics (n, mean, standard deviation, median, and range) at each time point and the change from baseline will be summarized by treatment group. Line plots of mean change from baseline, with standard error, over time will be displayed by treatment group.

A mixed effects model with repeated measures analysis will be conducted estimating change from baseline at each time point between two treatments. FAS subjects who have a baseline value and at least one post-baseline value are included in the analysis. Change from baseline will be fitted to a mixed effects model including subjects as a random effect, and baseline value, treatment group, time in treatment cycles, treatment-by-time interaction, and randomization stratification factor as fixed effects. A mean change between 5 and 10 points on the 1 to 100 scales of the EORTC QLQ-C30 and EORTC QLQ-MY20 has been defined as noticeable by subjects and regarded as a significant change or a meaningful change (EORTC Quality of Life Group).

For the key PRO endpoints, time to worsening and time to improvement will be derived. A distribution-based method will be used to define improvement/worsening in scores, i.e., half standard deviation away from the mean score at baseline combining both treatment groups.

Time to improvement will be summarized by using descriptive statistics such as mean, standard deviation, median and range.

Time to worsening will be estimated using Kaplan-Meier methods. The hazard ratio for daratumumab plus lenalidomide relative to lenalidomide and its associated 95% confidence interval (CI) will be calculated based on the stratified Cox proportional hazards model by the stratification factor at randomization. Death due to disease progression will be considered as worsening. Subjects who have not met the definition of worsening will be censored at the last PRO assessment. Subjects without baseline assessment or post-baseline assessment will be censored at date of randomization. A Kaplan-Meier figure for the key PRO endpoints will be generated to show time to worsening and censored subjects.

Other PRO endpoints

Other scales of EORTC QLQ-C30 and QLQ-MY20 include:

- EORTC QLQ-C30
 - functional scales: role, cognitive, emotional, and social
 - symptom scales: nausea and vomiting
 - single-item score: dyspnea, loss of appetite, insomnia, constipation, diarrhea, and financial difficulties
- QLQ-MY20

- side effects of treatment
- future perspective
- body image.

The change from baseline at each time point will be summarized descriptively by treatment group.

REFERENCES

Signature

User	Date	Reason

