11.3.2.2. Patient-reported Outcomes

The EORTC QLQ-C30 and EORTC QLQ-MY20 scale scores and EQ-5D-5L utility and visual analog scores will be descriptively summarized by treatment group at each time point. Withingroup and between-group treatment effects of the PRO endpoints will be assessed by change from baseline using mixed models for repeated measures. Full details on meaningful change thresholds and statistical analyses will be provided in the SAP.

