1.4. Sample Size Justification

Based on previous reports of MRD negativity rate in lenalidomide-treated myeloma patients, the anticipated MRD (at 10⁻⁵) negativity conversion rate is estimated to be 20% for patients treated with lenalidomide alone following post ASCT. Assuming a 20% absolute increase in MRD negativity rate (40% daratumumab plus lenalidomide versus 20% lenalidomide alone) by the end of 12-month maintenance treatment, a sample size of 214 patients (ie, 107 patients per treatment group at 1:1 randomization) will be needed to achieve at least 85% of power to detect such a treatment difference at a 2-sided alpha of 0.05 using continuity corrected chi-squared test.

Disease assessments for each patient will continue until 36 months from the date of randomization of the last patient. It is anticipated that this will yield 64 PFS events and provide approximately 79% power to detect a 50% reduction in the risk of progression or death (HR=0.50, translating to an improvement in median PFS from 60 months to 120 months) with a log-rank test at a 2-sided alpha of 0.05 with an accrual period of 1 year. One interim analysis using Obrien-Fleming alpha spending function is planned at the time of primary endpoint analysis when approximately 32 events are anticipated.

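### The PRO model states only a random subject effect for within-patient dependence; read literally this is compound symmetry, so visit-level confidence intervals and tests can be miscalibrated.

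*SAP*

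**What the plan says.** Protocol 11.3.2.2 says that PRO "treatment effects of the PRO endpoints will be assessed by change from baseline using mixed models for repeated measures" and leaves the full details to the SAP.

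SAP 7.1.2 introduces the analysis in similar terms: "A mixed effects model with repeated measures analysis will be conducted estimating change from baseline at each time point between two treatments". It then gives the model: "Change from baseline will be fitted to a mixed effects model including subjects as a random effect". The fixed effects are the baseline value, treatment group, "time in treatment cycles, treatment-by-time interaction, and randomization stratification factor as fixed effects". The random subject effect is the only within-patient term stated. Neither document gives a residual covariance structure, a fallback, robust standard errors or a degrees-of-freedom method.

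SAP 7.1.1 gives the schedule, "which will be measured at baseline, 6 months, 12 months, 24 months, and 36 months", and states "No imputation will be done for the PRO data". SAP 7.1.2 also places the PRO endpoints outside the testing hierarchy, without Type I error control.

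**The concern.** A random subject intercept with independent residuals, the usual default, gives every visit the same variance and every pair of visits the same correlation. Months 6 and 12 are then taken to be as closely related as months 6 and 36.

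The SAP asks for the treatment difference at each visit. Under this structure the standard error of each difference rests on a variance pooled over visits. It is too small where the true residual variance is above average and too large where it is below. With drop-out and no imputation, the late-visit estimates and their standard errors also depend on the assumed correlations between visits.

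Change in health-related quality of life is a listed secondary endpoint, so the calibration of its intervals matters even without alpha control. The study is also open-label. If the SAP leaves the covariance open, it can be chosen after the data have been seen.

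**Working it through.** The documents contain no PRO power, SD, correlation or retention figure, so there is no plan figure to reproduce.

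**Inputs from the documents.** Four post-baseline visits at 6, 12, 24 and 36 months (SAP 7.1.1); smallest gap 12 − 6 = 6 months, largest 36 − 6 = 30. Sample size 214, or 107 per arm (SAP 1.4). Two-sided tests (SAP 5.1.1).

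**Assumed inputs.** All SDs, correlations and retention rates. SDs are to be read as residual SDs given baseline, because the model adjusts for baseline. Visit is treated as a category.

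**Step 1: formula, complete data.** The model uses the mean of the four visit variances at every visit, so

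- model SE / true SE at visit j = √(mean variance / variance at j)
- actual two-sided error at visit j = 2 × [1 − Φ(1.96 × that ratio)]

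**Step 2: SD rising in equal steps by visit, month-6 SD set to 1.** For a 20% rise the SDs are 1, 1.067, 1.133 and 1.2. The mean variance is (1 + 1.138 + 1.284 + 1.44)/4 = 1.216 and the pooled SD is 1.103. The month-36 ratio is 1.103/1.2 = 0.919, and 1.96 × 0.919 = 1.80, which gives 7.2%.

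| Rise, month 6 to 36 | Pooled SD | Ratio, month 36 | Error, month 36 | Ratio, month 6 | Error, month 6 |
|---|---|---|---|---|---|
| 20% | 1.103 | 0.919 | 7.2% | 1.103 | 3.1% |
| 30% | 1.155 | 0.889 | 8.2% | 1.155 | 2.4% |
| 50% | 1.264 | 0.843 | 9.9% | 1.264 | 1.3% |

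If the SD instead rises linearly in calendar time, the month-36 errors are 7.4%, 8.5% and 10.5%, so the interpolation matters little.

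**Step 3: other directions, complete data.** Equal SDs give 5.0% at every visit. SDs falling 24/22/20/18 give 8.5%, 6.0%, 3.9% and 2.2% at months 6, 12, 24 and 36, the reverse pattern.

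**Step 4: simulation under the null.** 107 per arm, REML random-intercept fit, 3,000 runs per row. Correlation is 0.75 per 6 months and decays with time (0.75⁵ = 0.24 between months 6 and 36). Drop-out is random, with retention 100/95/80/65%.

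| Scenario | Error at 6 / 12 / 24 / 36 months | Mean model SE / empirical SD, month 36 |
|---|---|---|
| Equal SDs, complete | 5.4 / 4.9 / 5.3 / 5.1% | 0.998 |
| Equal SDs, drop-out | 4.9 / 4.9 / 5.4 / 6.7% | 0.937 |
| SDs 18/20/22/24, complete | 2.6 / 3.4 / 5.9 / 8.4% | 0.882 |
| SDs 18/20/22/24, drop-out | 2.6 / 4.1 / 7.1 / 10.3% | 0.821 |
| SDs 16/19/22/26, drop-out | 1.1 / 2.8 / 6.2 / 13.6% | 0.762 |
| SDs 24/22/20/18, drop-out | 7.8 / 5.1 / 4.0 / 2.7% | 1.112 |

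The first row shows that decaying correlation alone does no harm to visit-level tests when variances are equal and data complete.

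**Step 5: does the remedy work?** In 600 further runs (SDs 18 to 24, drop-out), the random-intercept model gave 3.5 / 4.7 / 6.7 / 10.7%. The unstructured covariance gave 6.0 / 5.5 / 4.0 / 5.7%, with a Monte Carlo standard error of about 0.9 percentage points.

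**The case against.** The strongest reply is that the SAP is under-specified, not wrong. It does not say that residuals are independent, and both documents use repeated-measures language. A reader might infer that the SAP imposes compound symmetry or breaks the protocol's commitment. The text supports neither, because it is silent on residual covariance and the two labels are compatible. This stands. It does not remove the point, because the protocol defers to the SAP and the literal model is the one described.

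A reader might also infer that late-visit tests are too liberal as a matter of fact. The documents give no PRO variances, and falling SDs would make the late tests conservative and the early ones liberal. Unequal spacing alone is no proof of harm either, as the equal-SD, complete-data row shows.

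A third tempting inference is that the plotted error bars are wrong. SAP 7.1.2 places the line plots with the descriptive statistics, before the model, so their standard errors appear to be raw. The point concerns model-based intervals and tests.

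Finally, the protocol's Time and Event Schedule Part 1 asks for PROs at the specified timepoints even after treatment stops. That should limit late missing data, and the 65% retention used above may be pessimistic. The equal-step figures in Step 2 do not depend on drop-out.

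**Conclusion.** The concern holds as a conditional one. The only stated within-patient structure, taken literally, is compound symmetry. Visit-level inference is then miscalibrated if residual variance given baseline differs by visit, or if decaying correlation combines with drop-out.

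Under an assumed 20% to 50% rise in SD with complete data, the error of a nominal 5% test is about 7% to 10% at month 36 and about 3% to 1% at month 6. In the assumed drop-out scenarios with equal or rising SDs, month-36 error runs from 6.7% to 13.6%. Falling SDs reverse the pattern, and equal SDs with complete data give no distortion.

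The consequence is small. It is confined to secondary PRO results without alpha control; the MRD and PFS analyses are untouched. The change is worth making because it is cheap and removes an open choice.

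**What to change.** In SAP 7.1.2, replace the random subject effect with an unstructured within-subject covariance over the four post-baseline visits. State that visit is categorical and that estimation is by REML with Kenward-Roger degrees of freedom. A baseline-by-visit term is optional.

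Pre-specify a fallback for non-convergence that allows unequal variances and respects the unequal spacing, such as a spatial power structure with heterogeneous variances. A simpler structure with robust sandwich standard errors is another option, though it corrects the standard errors and not the dependence of the estimates on the covariance under drop-out. Heterogeneous Toeplitz is not suitable: it gives the 6-to-12-month pair (6 months apart) the same correlation as the 12-to-24 and 24-to-36 pairs (12 months apart).

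The cost is a revised model statement and no new data. The unstructured matrix has 4 × 5/2 = 10 parameters, which is feasible with 214 patients. The small downside is the extra parameters and the possible need to use the fallback.

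### As written, PRO worsening and improvement are judged against the pooled baseline mean, not against each patient's own baseline

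*SAP*

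**What the plan says.** Protocol section 11.3.2.2 leaves meaningful-change thresholds to the SAP. SAP section 7.1.2 then states: "For the key PRO endpoints, time to worsening and time to improvement will be derived". The key endpoints are "EORTC-QLQ-C30 GHS, Physical Functioning, Fatigue, Pain subscales", the QLQ-MY20 disease symptoms scale, and the EQ-5D-5L utility score and VAS, seven measures in all. The threshold is described as distribution-based and set at "half standard deviation away from the mean score at baseline combining both treatment groups".

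Time to worsening gets Kaplan-Meier curves and a stratified Cox hazard ratio. Time to improvement gets descriptive statistics only. Death due to disease progression also counts as worsening. On censoring, the section says "Subjects who have not met the definition of worsening will be censored at the last PRO assessment" and "Subjects without baseline assessment or post-baseline assessment will be censored at date of randomization".

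Section 7.1.1 says the instruments are "measured at baseline, 6 months, 12 months, 24 months, and 36 months", and for the QLQ-C30 that "All scale and item scores will be linearly transformed to be in the range from 0 to 100". Section 7.1.2 also remarks that "A mean change between 5 and 10 points on the 1 to 100 scales" of the EORTC instruments is noticeable to patients, but does not link this to the time-to-event rule.

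**The concern.** The sentence names a reference point, and that point is the group mean at baseline over both arms. A programmer who follows it would compute one number per scale and compare every patient's score with it.

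That classifies level, not change. Take a scale on which low is bad:

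- A patient who enters 0.6 SD below the mean and stays there meets the worsening rule at the first follow-up.
- A patient who enters 1 SD above the mean must lose 1.5 SD before meeting it.
- Only a patient who enters exactly at the mean is treated as a half-SD change rule would treat them.

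Change in health-related quality of life is a listed secondary endpoint (protocol Table 1). In an open-label trial, curves labelled time to worsening will be read as deterioration on treatment. Under the literal rule they would be driven largely by where patients started.

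**Working it through.** **Is the rule corrected elsewhere?** Change from baseline appears in SAP 7.1.2 for the descriptive summaries, the line plots and the mixed model, and in the remark on 5 to 10 points of mean change. None of these is tied to the time-to-event definition. No rule covers patients already beyond the cut-off at baseline. The documents state no figure for how many that would be, so there is no plan figure to reproduce.

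**Share beyond the cut-off at baseline.** Inputs: cut-off at the pooled mean minus 0.5 SD (SAP 7.1.2); N = 214 (SAP 1.2); normal scores (assumed).

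P(Z < -0.5) = 0.3085, and 0.3085 × 214 = 66 patients. By symmetry the same share lies beyond the improvement cut-off, so 2 × 0.3085 = 62% start beyond one or the other.

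The EORTC scales are bounded and discrete, so normality is only a starting point. Assumed beta distributions on 0 to 100, rounded to discrete levels, give:

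| Illustrative shape (assumed) | Worsened side | Improved side |
|---|---|---|
| Global-health-like, Beta(5, 2.2), 13 levels | 31% | 32% |
| Physical-functioning-like, Beta(5, 1.2), 16 levels | 22% | 32% |
| Fatigue-like, Beta(1.5, 3), 10 levels | 37% | 45% |
| Pain-like, Beta(0.6, 1.8), 7 levels | 23% | 33% |
| Pain-like, heavy floor, Beta(0.3, 1.5), 7 levels | 25% | 55% |
| Symmetric, Beta(3, 3), 13 levels | 28% | 27% |

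**Classification at one later visit.** Let baseline b be standard normal and follow-up f = ρb + √(1 − ρ²)·e, with e standard normal and ρ the between-visit correlation (assumed). The literal rule flags f ≤ -0.5. The own-baseline rule flags f − b ≤ -0.5. Columns 2 to 5 assume no true mean change. Columns 6 and 7 take patients with b > 1, subtract a true decline of 1 SD from f, and count those not flagged.

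| ρ | Flagged, literal | Flagged, own baseline | Literal flags without a 0.5 SD fall from own baseline | Falls of ≥0.5 SD that the literal rule misses | High starters missed, literal | High starters missed, own baseline |
|---|---|---|---|---|---|---|
| 0.4 | 31% | 32% | 43% | 45% | 55% | 7% |
| 0.5 | 31% | 31% | 47% | 47% | 61% | 8% |
| 0.6 | 31% | 29% | 52% | 49% | 69% | 9% |
| 0.75 | 31% | 24% | 63% | 52% | 81% | 9% |
| 0.9 | 31% | 13% | 81% | 56% | 94% | 7% |

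**Effect on the hazard ratio.** Assume a treatment benefit of 0.3 SD at one visit and approximate the hazard ratio by ln(1 − p₁)/ln(1 − p₀), where p₁ and p₀ are the flagged shares with daratumumab and with lenalidomide alone.

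- Literal rule: p₀ = Φ(-0.5), p₁ = Φ(-0.8), giving 0.645 whatever ρ is.
- Own-baseline rule: change has SD √(2 − 2ρ), so p₀ = Φ(-0.5/√(2 − 2ρ)) and p₁ = Φ(-0.8/√(2 − 2ρ)). The result is about 0.68 at ρ = 0.4, 0.645 at 0.5, 0.60 at 0.6 and 0.50 at 0.75.

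The two rules coincide at ρ = 0.5, where the change SD is exactly 1. The literal rule gives the weaker effect only above that.

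**The case against.** The strongest reply is that the sentence is compressed wording for a change of half the pooled baseline SD. Improvement and worsening are words about change, the key scales are otherwise analysed as change from baseline, and patients without a baseline assessment are censored at randomization, which a fixed cut-off would not need. This reading is plausible and may be what the sponsor means. It does not settle the matter, because the stated reference point is the group mean and no sentence says otherwise. Two programmers could build different endpoints from this text.

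A reader might infer that about a third of patients have an event on day one. The SAP does not say so: no rule counts a baseline score as an event, and patients with no post-baseline assessment are censored at randomization. Patients beyond the cut-off would count at the first post-baseline PRO, month 6, if they had not recovered.

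A reader might also infer that the hazard ratio must be diluted or biased. Randomization balances starting level in expectation, so the comparison between arms is not biased on this account. Dilution relative to an own-baseline rule depends on a correlation that the documents do not give, for visits 6 to 12 months apart.

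The own-baseline rule has its own weakness. Among patients starting more than 1 SD above the mean with no true change, regression to the mean would flag about 43% at ρ = 0.75 and about 61% at ρ = 0.5.

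Finally, SAP 7.1.2 puts the PRO endpoints outside the testing hierarchy, without Type I error control.

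**Conclusion.** The point stands as a fault in the stated definition, with limited reach. Followed literally, the rule measures score level: with no true change and ρ between 0.4 and 0.9, 43% to 81% of those flagged at a later visit have not fallen half an SD from their own baseline. About 31% of patients would start beyond the worsening cut-off if scores are normal, and 22% to 37% under the bounded shapes tried. Every one of these figures rests on assumed distributions and correlations. In particular, 31% should not be read as a property of this trial's data.

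The affected outputs are the time-to-worsening curves and hazard ratios and the time-to-improvement summaries for the seven key measures. The baseline-adjusted mixed model of change is unaffected, and no primary, PFS, OS or safety conclusion depends on the rule. It should be corrected because the outputs would not mean what their titles say.

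**What to change.** Replace the threshold sentence in SAP 7.1.2 with a rule that defines worsening or improvement as a post-baseline change from the patient's own baseline of at least 0.5 × the SD of baseline scores pooled over both arms. The direction should be given for each scale: lower is worse for global health, functioning, utility and VAS; higher is worse for fatigue, pain and disease symptoms. State how patients are handled whose baseline is too close to the floor or ceiling for a change of that size to be possible.

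If a fixed cut-off was intended, the SAP should say so, describe the endpoint as reaching a score level, and state what happens to patients already beyond the cut-off at baseline.

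The cost is one or two sentences and a small programming change. No new data are needed.
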